During the neoadjuvant treatment, diagnosis of disease progression should be confirmed by clinical, laboratory, radiological, and/or histological findings. After surgery, prior to commencing adjuvant treatment or observation, the first planned tumor assessment will be performed in Week 13 to conclude the neoadjuvant therapy-surgery intervention window and should include a CT scan. After the treatment phase, during the follow-up phase, all patients must be followed to assess disease recurrence and survival as outlined for each arm in the schedules of activities (see Sections [A11–6](#) [Nivo + Ipi], [A12–6](#) [RO7247669 2100 mg], [A13–6](#) [Atezo + Tira], [A14–6](#) [RO7247669 2100 mg + Tira Cohort 1], [A15–6](#) [RO7247669 600 mg], and [A16–6](#) [RO7247669 600 mg + Tira]). *Tumor assessments that have been performed outside the protocol-mandated time window do not have to be repeated. However, at the investigator's discretion, tumor assessments may be repeated at any time if progressive disease is suspected.*

The designation of disease recurrence, whether local, regional, or distant, can be made only when clinical, laboratory, radiological and/or histological findings confirm the diagnosis.

During the post-surgery period, disease status should be clinically evaluated and documented every 3 months for the first 2 years; every 6 months in the third year and annually thereafter until a diagnosis of a recurrence (defined below). In addition to physical examinations, liver function tests, bone scans, chest X-ray/diagnostic CT scan, liver imaging, and/or other radiographic modalities may be considered when clinically indicated to exclude metastatic disease within timelines as per current local standard of practice.

The diagnosis of a progression or recurrence should be confirmed histologically whenever clinically possible. The earliest date of diagnosis of disease progression or

recurrent disease should be used and recorded. This date should be based on objective clinical, radiological, histological, or cytological evidence. Recurrent disease includes local, regional, or distant recurrence: local recurrence is defined as tumor regrowth within 2 cm of the primary lesion's tumor bed; regional recurrence as any nodal or non-nodal tumor lesions that are more than 2 cm from the primary lesion but are not beyond the regional nodal basin; distant recurrence as any non-local/non-regional recurrence.

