6.4 EFFICACY ANALYSES

6.4.1 Primary Efficacy Endpoint in Cohort 1

The primary efficacy endpoint in Cohort 1 is pRR at time of surgery. pRR will be assessed after completion of neoadjuvant treatment (Week 7) at time of CLND.

The pRR is defined as the proportion of patients who achieve pCR (a complete absence of viable tumor in the treated tumor bed), pathologic near complete response (pnCR; <10% of viable tumor in the treated tumor bed); and pathologic partial response (pPR; <50% of the treated tumor bed is occupied by viable tumor cells) as determined by independent pathologic review. Patients with missing or no pathologic response assessment, *including patients who do not proceed to CLND*, will be classified as non-responders.

pRR will be calculated for each arm along with 95% CIs (Clopper-Pearson method). The difference in pRR between the experimental arms and the control arm will also be calculated, along with 95% CIs using the Wald method with continuity correction.

6.4.2 Secondary Efficacy Endpoints in Cohort 1

The secondary efficacy endpoints in Cohort 1 are pRR at time of surgery as determined by local pathologic assessment, event-free survival (EFS), RFS, OS, and ORR prior to surgery. pRR is defined in Section [6.4.1](#).

EFS is defined as the time from randomization to any of the following events (whichever occurs first): disease progression that precludes surgery, as assessed by the investigator according to RECIST v1.1 (see Section [4.5.7](#)); local, regional, or distant disease recurrence; or death from any cause. Patients who have not experienced such events will be censored at the time of their last post-tumor tumor assessment.

RFS is defined as the time from surgery to the first documented recurrence of disease or death from any cause. For patients who do not have documented recurrence of disease or death, RFS will be censored at the day of the last tumor assessment.

OS is defined as the time from randomization to death from any cause. Patients who are still alive at the time of OS analysis will be censored at the last date they were known to be alive.

The Kaplan-Meier method will be used to estimate the median for RFS, EFS, and OS, 95% CIs will be constructed using the Brookmeyer and Crowley method. The RFS, EFS, and OS rate at specific timepoints will also be estimated using the Kaplan-Meier method, with 95% CIs calculated on the basis of Greenwood's estimate for the variance.

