The ORR according to RECIST v1.1 will be assessed after completion of neoadjuvant treatment (Week 7) and is defined as the proportion of patients with a CR or PR, as determined by the investigator according to RECIST v1.1. Patients with missing or no response assessments will be classified as non-responders. Note that ORR will be determined using unconfirmed pre-operative radiologic responses. Although RECIST v1.1 requires confirmatory imaging assessments to be completed at least 4 weeks after the initial response, due to the timing of CLND, these responses cannot be confirmed with subsequent imaging.

ORR will be calculated for each arm, along with 95% CIs (Clopper-Pearson method). The difference in ORR between the experimental arms and the control arm will also be calculated, along with 95% CIs using the Wald method with continuity correction.

6.4.3 Exploratory Efficacy Endpoints in Cohort 1

The exploratory efficacy endpoints in Cohort 1 are landmark EFS, landmark RFS, and landmark OS at specific timepoints (1, 2, 3, and 5 years). RFS, EFS, and OS are defined in Section [6.4.2](#).

Landmark EFS rates, landmark RFS rates, and landmark OS rates will be estimated for each study arm using the Kaplan-Meier method, with 95% CIs calculated through use of Greenwood's formula.

6.4.4 Primary Efficacy Endpoint in Cohort 2

The primary efficacy endpoint in Cohort 2 is ORR, as defined in Section [2](#) (see [Table 3](#)). ORR is determined by the investigator according to RECIST v1.1. Patients with missing or no response assessments will be classified as non-responders.

ORR, the proportion of patients with a complete or partial response, will be calculated for each arm, along with 95% CIs (Clopper-Pearson method).

6.4.5 Secondary Efficacy Endpoints in Cohort 2

The secondary efficacy endpoints in Cohort 2 are PFS, OS, OS at specific timepoints (e.g., 6 months), duration of response (DOR), and disease control, as defined in Section [2](#) (see [Table 3](#)). PFS, DOR, and disease control are determined by the investigator according to RECIST v1.1.

DOR will be derived for efficacy-evaluable patients with a CR or PR.

For patients who do not have documented disease progression or death, PFS and DOR will be censored at the day of the last tumor assessment.

Patients who are still alive at the time of OS analysis will be censored at the last date they were known to be alive.

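### Censoring RFS and EFS at the last tumor assessment can understate both curves if post-surgery follow-up is mainly clinical, and the EFS rule cannot be applied as worded

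*Combined protocol and SAP*

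**What the plan says.** **Censoring.** For RFS, Section 6.4.2 says: "For patients who do not have documented recurrence of disease or death, RFS will be censored at the day of the last tumor assessment". For EFS it says: "Patients who have not experienced such events will be censored at the time of their last post-tumor tumor assessment". Neither end point of follow-up is defined.

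**Follow-up.** Section 4.5.7.2 fixes one scan after surgery: "the first planned tumor assessment will be performed in Week 13 to conclude the neoadjuvant therapy-surgery intervention window and should include a CT scan". After that, "disease status should be clinically evaluated and documented every 3 months for the first 2 years; every 6 months in the third year", then yearly. On imaging in this period it says that "other radiographic modalities may be considered when clinically indicated to exclude metastatic disease within timelines as per current local standard of practice".

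**Events.** The same section lets a recurrence be dated from clinical findings, imaging, histology or cytology. Death from any cause counts whenever it occurs.

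**Schedules.** Section 4.5.7.2 refers to the schedules of activities in the arm appendices for the follow-up detail. Those tables are not in the text available for this review.

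**The concern.** An event can come from any kind of evidence, but an event-free patient may be credited only up to the last scan. Take a patient seen in clinic every 3 months, last scanned at 12 months, whose follow-up ends at 23 months. If recurrence is found clinically at 18 months, the patient is an event at 18 months. If the patient is documented free of recurrence at 21 months, the patient is censored at 12 months. Time at risk is then removed only from patients who did not fail. Kaplan-Meier requires censoring that is unrelated to outcome, and this breaks the requirement in one direction: the hazard is overstated and the curve is too low.

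At stake are the RFS and EFS medians and rates (secondary) and the 1-, 2-, 3- and 5-year landmark rates (exploratory).

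**Working it through.** The plan gives no expected RFS or EFS figure, so there is nothing to reproduce. The check asks how far the estimate moves when the censoring date changes and nothing else does.

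**Inputs from the documents.** Clinical visits every 3 months to year 2, every 6 months in year 3, then annually; a CT at Week 13, about 6 weeks after surgery (Section 4.5.7.2).

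**Assumptions.** Exponential RFS with a true 2-year rate of 80%. Section 3.4.4 cites more than 80% for the control regimen without a time point, and Section 3.4.5 cites 2-year RFS of 89% with pCR and 50% without, so rates from 50% to 90% were also run. Recurrence is detected at the next scheduled visit. Follow-up is uniform over 1–4 years (mature) or 0.5–2.5 years (immature). The imaging interval is not in the documents, so it is varied.

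**Hand calculation: mature follow-up, scans every 12 months.**

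- Chance of recurrence per 3 months: q = 1 − 0.80^(1/8) = 0.02751. RFS at 1 year: 0.80^(1/2) = 0.8944. Everyone has at least 1 year of follow-up, so there is no distortion before then.
- Scale to the patients recurrence-free at 1 year (= 1). Two thirds have at least 2 years of follow-up. Of the other third, those who stay recurrence-free are censored at the 1-year scan. Those who recur within their follow-up stay in until their event: 0.02751×0.25 + 0.02751×0.97249×0.1667 + 0.02751×0.94574×0.0833 = 0.0135.
- Risk set at 1.25 years: 0.6667 + 0.0135 = 0.6802. Each later risk set is the previous one minus its events.

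| Visit (years) | Events | At risk | Factor |
|---|---|---|---|
| 1.25 | 0.02751×0.9167 = 0.0252 | 0.6802 | 0.9629 |
| 1.50 | 0.02751×0.9725×0.8333 = 0.0223 | 0.6550 | 0.9660 |
| 1.75 | 0.02751×0.9457×0.75 = 0.0195 | 0.6327 | 0.9692 |
| 2.00 | 0.02751×0.9197×0.6667 = 0.0169 | 0.6132 | 0.9725 |

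Estimated 2-year RFS = 0.8944 × 0.9629 × 0.9660 × 0.9692 × 0.9725 = 0.784. With censoring at the last clinical visit, every factor is 1 − q = 0.9725, which gives 0.8944 × 0.9725⁴ = 0.800.

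**Simulation of the same model, 200,000 patients per scenario (estimated 2-year RFS, %).**

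| True | Follow-up | Scan every 3 mo | 6 mo | 12 mo |
|---|---|---|---|---|
| 90 | mature | 90.0 | 89.7 | 89.0 |
| 90 | immature | 90.0 | 88.8 | 85.9 |
| 80 | mature | 79.9 | 79.5 | 78.4 |
| 80 | immature | 79.9 | 77.9 | 72.6 |
| 50 | mature | 50.0 | 49.1 | 47.2 |
| 50 | immature | 49.8 | 46.2 | 38.4 |

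At a true rate of 80%, the understatement with 6- to 12-monthly scans runs from 80 − 79.5 = 0.5 to 80 − 72.6 = 7.4 points. Censoring at the last disease-status evaluation gives 79.8–80.0% in every one of these scenarios.

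**Sparser imaging (assumed fractions, none from the documents).** In a separate run, each event-free patient is either scanned at every visit or never after Week 13, and follow-up is uniform over 24–48 months. If 75%, 50% or 25% are scanned, a true 80% is estimated at about 76%, 70% or 58%.

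**When the bias vanishes.** It disappears if the term covers the clinical visits, or if recurrences are found only at regular 6- or 12-monthly scans (79.9–80.0% in the same runs).

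**How arms could diverge.** With a true 80% in both arms, 12-monthly scans with mature against immature follow-up give 78.4 − 72.6 = 5.8 points. Immature follow-up with 6- against 12-monthly scans gives 77.9 − 72.6 = 5.3 points.

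**The case against.** **The schedules may settle it.** Section 4.5.7.2 calls the Week 13 assessment the first planned one, and its follow-up text mentions a prescribed window for tumor assessments. Both suggest that later scans may be scheduled. This stands: the bias is conditional on tables not seen here.

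**The term may be broader than imaging.** Section 4.5.7.2 also uses it for the pathology at surgery, and Appendix 1 allows caliper measurement. Against that, Section 4.5.7.1 treats the screening assessment as CT or MRI, Week 13 should include a CT, and Appendix 9 (A9-3) expects a chest CT at every tumor assessment. Imaging is the more natural reading but not the only one.

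**A reader might infer negative RFS times** for patients not assessed after surgery. The documents do not support that firmly: because the surgical pathology is itself called a tumor assessment, such a patient can be placed at time zero. A floor is sensible housekeeping, not evidence of bias.

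**The realistic bias is small against sampling error.** Section 6.1 plans 20–60 patients per experimental arm. At 80%, before censoring, 1.96 × √(0.8 × 0.2/n) is 17.5 points for n = 20 and 10.1 for n = 60. That is true, but a confidence interval does not correct a systematic shift, and this one is nearly free to remove.

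**Imaging-based censoring is a defensible convention** where occult visceral recurrence is possible. That is a reason to keep it as a sensitivity analysis.

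**Conclusion.** The concern holds in conditional form. If the term means imaging and the arm schedules do not require a scan at each visit, RFS and EFS are biased downward. At 2 years the size is about 0.5 to 7 points with 6- to 12-monthly imaging and a true rate of 80%, both assumed. It is more if many patients have no scan after Week 13, and negligible if scans follow the 3-monthly visits. The EFS wording is unusable whichever way this falls.

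A reader might infer that the curves are certainly too low, or that some arms are penalized more than others. The documents support neither. Section 4.5.7.2 applies one follow-up rule to all Cohort 1 arms, and nothing available links imaging frequency to arm, adjuvant choice or pathologic response. A difference is possible because arms open at different times (Section 4.2) and imaging follows local practice, but it is not shown.

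Primary pRR and OS are unaffected. Section 6.1 plans no hypothesis test, and the Cohort 1 expansion example in Section 6.9 uses pRR. Severity: moderate.

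**What to change.** 1. Check the follow-up part of the arm schedules and state in Section 6.4.2 what *tumor assessment* means.
2. Replace both censoring sentences in Section 6.4.2 with: *Patients without an event are censored at the last documented disease-status evaluation, clinical or radiographic, showing no progression or recurrence. If there is none after randomization (EFS) or surgery (RFS), they are censored at that date.*
3. Keep imaging-only censoring as a sensitivity analysis.
4. Housekeeping for Cohort 2: Section 6.4.5 states that "PFS and DOR will be censored at the day of the last tumor assessment". Scans there are scheduled every 9 and later every 12 weeks, so the rule suits the follow-up. PFS only needs a floor at randomization or enrollment for patients with no post-baseline scan.

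The cost is a few sentences and one extra analysis, using visits already scheduled. The downside is that clinical evaluation is less sensitive than imaging, so occult recurrences may be dated slightly later. The sensitivity analysis shows how much the choice of censoring date matters.

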6.5 SAFETY ANALYSES

Verbatim adverse event terms will be mapped to Medical Dictionary for Regulatory Activities thesaurus terms, and adverse event severity will be graded according to NCI CTCAE v5.0 and also according to the ASTCT CRS Consensus Grading Scale for CRS.

Safety will be assessed through summaries of adverse events, changes in laboratory test results, changes in vital signs and ECGs, and exposure to study drugs. Exposure to combination treatment and length of safety follow-up will be summarized by treatment arm.

All verbatim adverse event terms will be mapped to Medical Dictionary for Regulatory Activities thesaurus terms. Adverse event severity will be graded according to NCI CTCAE v5.0, and severity of CRS will also be graded by the investigator according to the ASTCT Consensus Grading (Lee et al. 2019). All adverse events, serious adverse events, adverse events leading to death, adverse events of special interest, and adverse events leading to study treatment discontinuation that occur on or after the first dose of study treatment (i.e., treatment-emergent adverse events) will be summarized by mapped term, appropriate thesaurus level, and severity grade. For events of varying severity, the highest grade will be used in the summaries. Deaths and causes of death will be summarized.

Relevant laboratory, vital sign (pulse rate, respiratory rate, blood pressure, pulse oximetry, and temperature), and ECG data will be displayed by time, with grades identified where appropriate. Additionally, a shift table of selected laboratory test results will be used to summarize the baseline and maximum postbaseline severity grade. Changes in vital signs and ECGs will be summarized.

Additionally, in Cohort 1, the incidence, nature of immune-related adverse events Grade ≥ 3 during the first 12 weeks, and the rate and duration of delayed surgery due to treatment-related adverse events will be summarized by treatment arm. CLND may be delayed for up to 2 weeks if study treatment-related adverse events have not improved sufficiently at the time of planned surgery (see Section 3.1.3).

Additionally, surgical complications will be scored according to Clavien-Dindo classification ([Appendix 5](#)). Complication rates for every grade will be reported and scored for patients that underwent CLND.

6.6 PHARMACOKINETIC ANALYSES

Sparse samples will be collected for PK analyses of atezolizumab (patients who receive at least one dose of atezolizumab) and specified drugs given either alone or in

combination with atezolizumab (patients who receive at least one dose of the drug). Serum or plasma concentrations of the various study drugs will be reported as individual values and summarized (mean, standard deviation, coefficient of variation, median, range, geometric mean, and geometric mean coefficient of variation) by treatment arm and by cycle and day when appropriate and as data allow. Individual and median serum or plasma concentrations of the various study drugs will be plotted by treatment arm and cycle and day. PK data for combination drugs may be compared with available historical data from internal and published previous studies. Atezolizumab or other study drug concentration data may be pooled with data from other studies using an established population PK model to derive PK parameters such as clearance, volume of distribution, and area under the curve.

The relationship between PK parameters and safety, efficacy, PK, and biomarker endpoints may be analyzed and reported via descriptive statistics.

6.7 IMMUNOGENICITY ANALYSES

Immunogenicity may be assessed for atezolizumab and other study treatments as appropriate (refer to arm-specific appendices for details). The immunogenicity analyses will include all patients with at least one anti-drug antibody (ADA) assessment. Patients will be grouped according to treatment received or, if no treatment is received prior to study discontinuation, according to treatment assigned.

For atezolizumab, the numbers and proportions of ADA-positive patients and ADA-negative patients at baseline (baseline prevalence) and after drug administration (postbaseline incidence) will be summarized by treatment group. When determining postbaseline incidence, patients are considered to be ADA positive if they are ADA negative or have missing data at baseline but develop an ADA response following study drug exposure (treatment-induced ADA response), or if they are ADA positive at baseline and the titer of one or more postbaseline samples is at least 0.60-titer unit greater than the titer of the baseline sample (treatment-enhanced ADA response). Patients are considered to be ADA negative if they are ADA negative or have missing data at baseline and all postbaseline samples are negative, or if they are ADA positive at baseline but do not have any postbaseline samples with a titer that is at least 0.60-titer unit greater than the titer of the baseline sample (treatment unaffected).

For other study treatments where ADA is tested, positivity will be determined according to standard methods established in previous studies of that drug.

The relationship between ADA status and safety, efficacy, PK, and biomarker endpoints may be analyzed and reported via descriptive statistics.

6.8 BIOMARKER ANALYSES

Exploratory biomarker analyses will be performed in an effort to understand the association of these biomarkers with response to study drugs, taking into account efficacy and safety endpoints (see Section 4.5.9 for more details).

6.9 INTERIM ANALYSES

Given the exploratory nature of this study, it is anticipated that interim analyses will be conducted during the study, with the earliest interim analysis taking place when at least one experimental arm has completed enrollment in the preliminary phase, and patients have completed their pathologic response assessment (Cohort 1), or when at least one experimental arm has completed enrollment in the preliminary phase and patients have been followed for a minimum of 9 weeks for the primary endpoint analysis (ORR) (Cohort 2). Further interim analyses may be conducted as deemed appropriate by Sponsor. In Cohort 1, a posterior probability may be used to guide further enrollment based on the interim analysis of clinical activity in the experimental arm compared with the control arm. If the interim analysis suggests that the activity in an experimental arm is higher than that in the control arm, for example, the posterior probability of having a pRR improvement (e.g., 10%) is greater than a threshold (e.g., 70% confidence level), there may be further enrollment of 20 additional patients in the experimental arm (expansion phase).

In Cohort 2, a posterior probability may be used to guide further enrollment in a treatment arm based on an interim analysis of clinical activity in the experimental arm compared with a predefined ORR threshold, defined as an improvement over standard of care. For example, if available data suggest a standard of care ORR of 10%, and an ORR improvement of 10% is considered to be a clinical meaningful change, this would lead to an ORR threshold of 20% in the calculation of the posterior probability.

The ORR for standard of care treatment will be based on emerging internal and external data for in-class immune-modulating investigational and other compounds for the patient population in Cohort 2 who have received at least two lines of prior treatment at the time of the analysis.

The Sponsor may make a decision to expand enrollment in an arm based on the totality of available data including, but not limited to, duration of the observed responses, PFS, and potentially early OS data. Safety and biomarker data (available at the time of making this decision) will also be taken into consideration from the perspective of an adequate benefit-risk assessment.

The interim analyses will be performed and interpreted by Sponsor study team personnel.

